### B1. PURPOSE OF PROTOCOL

*We hypothesize that, compared to placebo, exposure to intravenous (IV) NSAID (ketorolac) impairs platelet function of healthy mothers undergoing elective cesarean delivery.*

### B2. SIGNIFICANCE AND BACKGROUND FOR THE STUDY

*Cesarean delivery has become the most common surgical procedure in the US, with over 1.2 million cesarean deliveries performed each year. The addition of non-steroidal anti-inflammatory drugs (NSAIDs) to a post-cesarean analgesic regimen has been shown to improve the quality of post-cesarean analgesia and markedly reduce opioid consumption. As a result, fewer patients incur opioid related side-effects such as nausea and vomiting, respiratory compromise, sedation, and impaired breast-feeding.*

*The effect of NSAIDs on healthy volunteers is relatively well-described. Most commonly, NSAIDs inhibit membrane-bound cyclooxygenase 1 (COX-1), the enzyme responsible for the production of the platelet agonist thromboxane A2. This ultimately results in inhibition of platelet aggregation and prolonged bleeding time. However, in the obstetric population, the presence and degree of platelet inhibition after NSAID exposure is less clear. This has limited the incorporation of NSAIDs into protocols for postpartum analgesia following cesarean delivery.*

*PFA-100 assays, with collagen/epinephrine and collagen/ADP as agonists, can reliably test for platelet inhibition. PFA has been utilized to examine the anti-platelet effects of platelet inhibitors including NSAIDs in studies involving non-obstetric patients. Thromboelastography (TEG) has been shown in numerous studies to represent in-vivo clot strength and function.*

*Research in this field is needed as physiologic changes of pregnancy combined with significant surgical blood loss and hemodilution at cesarean delivery may alter the effect on maternal platelet function. This has become more pressing as postpartum thromboprophylaxis is likely to be more commonly considered for patients after cesarean delivery. In their most recent unofficial guidelines, the American Society of Regional Anesthesia state that NSAIDs should not be used with thromboprophylaxis after patients received neuraxial blockade (ASRA App). However, to the best of our knowledge, there is limited data, only utilizing bleeding time, examining the potential platelet inhibitory effect of NSAIDs in a low-risk healthy cohort undergoing cesarean delivery.*

**B3. DESCRIPTION OF RESEARCH PROTOCOL****A. Study Design – Overview, Methods, Procedures****Study Design**

Prospective, randomized, double-blind, placebo-controlled trial.

**Endpoints:**

Primary outcome: Platelet Aggregometry (ADP-agonist) will be performed before (baseline obtained at completion of the case) and 10 min after IV dosing of study drugs. The timing of the post-dose blood draw was selected because the maximum concentration (Cmax) of IV ketorolac is  $2.9 \pm 1.8$  minutes and known platelet inhibition correlates closely with Cmax.

Secondary outcomes: Platelet Aggregometry (AA-agonist), Thromboelastographic indices (TEG), including R time, K time, alpha angle, and maximum amplitude, TEG platelet mapping MA for AA and ADP, Platelet phosphorylation (pDrp1), laboratory coagulation indices (PT, PTT, INR, fibrinogen). TEG will be performed using a Thromboelastography® 6S analyzer (Haemoscope Corp. Niles, IL), TEG will be performed before (baseline obtained pre-operatively) and platelet phosphorylation (pDrp1) will be performed by PlateletDiagnostics (Allston, MA). Relevant clinical data will also be collected, including: total estimated blood loss, total volume of intravenous fluid given during the intraoperative period.

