## **B. Statistical Considerations**

### ***Sample Size Justification:***

Based on available data from a prior study examining platelet inhibition of non-opioid analgesics, 10 a PFA closure time  $\geq 173$  seconds can be used to classify platelet inhibition. Using the aforementioned data on epinephrine-induced PFA closure time, 10 we estimate that, before and after ketorolac exposure, 25% and 70% patients respectively would exhibit prolonged PFA closure times. With an alpha error of 0.05 and a beta error of 0.8, we estimated that a sample size of 14 patients per group would provide 80% power.

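### ADP-agonist aggregometry is the sole primary outcome without a stated reason, although the AA-agonist assay, ranked secondary, tests the protocol's own COX-1 mechanism directly; a real ketorolac effect could be missed in the primary conclusion

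*Combined protocol and SAP*

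**What the plan says.** The hypothesis (B1) is broad: compared with placebo, "exposure to intravenous (IV) NSAID (ketorolac) impairs platelet function of healthy mothers undergoing elective cesarean delivery". It names no agonist and no pathway.

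The background (B2) gives one mechanism: "NSAIDs inhibit membrane-bound cyclooxygenase 1 (COX-1), the enzyme responsible for the production of the platelet agonist thromboxane" A2. It says that this ends in reduced aggregation and a longer bleeding time, again without naming an agonist.

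Under Endpoints (B3.A), the only primary outcome is ADP-agonist aggregometry: "Primary outcome: Platelet Aggregometry (ADP-agonist) will be performed before" and 10 minutes after study drug. The AA-agonist version opens the next list: "Secondary outcomes: Platelet Aggregometry (AA-agonist", followed by the thromboelastography (TEG) indices, TEG platelet mapping for both AA and ADP, pDrp1 and coagulation tests.

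The nearest text to a rationale for ADP is in B2: "PFA-100 assays, with collagen/epinephrine and collagen/ADP as agonists, can reliably test for platelet inhibition". That concerns the PFA-100, which is a different assay, and it names epinephrine alongside ADP.

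The sample size (B3.B) rests on a third measure: "Using the aforementioned data on epinephrine-induced PFA closure time". PFA closure time is not among the listed outcomes.

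Data Analysis (B3.B) provides unpaired t or Mann-Whitney tests between groups. It gives no testing order, no multiplicity rule, and no rule for the case where ADP and AA disagree.

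**The concern.** The primary outcome decides how the trial answers its hypothesis. Arachidonic acid is converted by COX-1, so AA-induced aggregation depends on the enzyme that B2 says NSAIDs block. ADP acts on platelets through its own receptors, with thromboxane as an amplifier. This is general pharmacology and is not stated in the protocol. On that footing, the plan's confirmatory test uses the assay that is matched less closely to its stated mechanism, and the better matched one sits in a long list of secondary outcomes with no testing order.

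The stake is interpretive. B2 and B5 motivate the trial by NSAID use alongside postpartum anticoagulation. A null primary result would be open to reading as reassurance on a bleeding question. A positive AA result could then be discounted as one of many unadjusted secondary findings.

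**Working it through.** **1. The plan's own figure.** B3.B gives 14 per group for 80% power, 25% versus 70% prolonged closure times, alpha 0.05 with sidedness not stated. The pooled normal formula is

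n = [z_α √(2p̄(1−p̄)) + z_β √(p₁(1−p₁) + p₂(1−p₂))]² / (p₂−p₁)²

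with p̄ = 0.475, √(2 × 0.475 × 0.525) = 0.706 and √(0.1875 + 0.21) = 0.630.

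- One-sided: (1.645 × 0.706 + 0.842 × 0.630)² / 0.45² = 14.1, or 15 rounded up. Power at 14 is 79.6%.
- Two-sided: (1.960 × 0.706 + 0.842 × 0.630)² / 0.45² = 18.1, or 19 rounded up. Power at 14 is 68.3%.

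So 14 is close to reproducible under a one-sided test, which the plan does not state. With the planned 20 per arm, two-sided power for 25% versus 70% is 84%. None of this carries over to either aggregometry endpoint: the calculation concerns a different assay, agonist and scale.

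**2. What 20 per arm can detect on the primary outcome.** Inputs from the documents: 20 per arm, unpaired t test, alpha 0.05. Assumption: two-sided. The documents give no SD, expected effect or meaningful difference for ADP or AA aggregometry, so the effect is expressed as d, the group difference divided by the SD of whatever measure is analysed (post-dose value or change).

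Noncentrality = d √(n/2) = d √10 = 3.162 d, with 38 degrees of freedom and critical value 2.024.

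| Assumed d | Noncentrality | Power |
|---|---|---|
| 0.3 | 0.95 | 15% |
| 0.5 | 1.58 | 34% |
| 0.8 | 2.53 | 69% |
| 0.91 | 2.87 | 80% |
| 1.0 | 3.16 | 87% |

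The 0.91 SD threshold follows from the group size alone. Which row applies to ADP cannot be determined from the documents. The table applies equally to AA, whose effect is not given either.

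**3. Side by side.** Mechanism (B2): COX-1 and thromboxane. Assay that runs through COX-1: AA aggregometry, secondary. Primary assay: ADP aggregometry, with no rationale. Power basis: epinephrine PFA closure time, which supports neither. The four do not line up, and only the ranking and the sample-size text need changing to align them.

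**The case against.** The strongest defence is that B1 asks about platelet function, not COX-1 activity. An assay that does not depend wholly on the blocked enzyme is a legitimate functional endpoint, arguably closer to whether inhibition extends beyond the expected pathway. That stands as a possible rationale, but the protocol does not state it, and B1 poses the wider question. This is why the fix below allows ADP to remain primary if the reason is given.

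Second, the documents nowhere say that ADP aggregation is less sensitive to ketorolac than AA aggregation. This also stands. That AA is the COX-1 substrate is basic pharmacology, but the size of any loss of sensitivity with ADP is not available here.

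Third, AA effects would be measured anyway, in aggregometry and in TEG platelet mapping. This stands too, and it limits the harm to the primary conclusion.

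A reader might infer from the lower rows of assumed effects that a null primary result is likely, or that the trial will report no impairment. The documents support neither. An ADP effect of 0.8 or 1.0 SD is not excluded and would give 69% or 87% power. How the authors would report discordant results is unknown, because the plan has no rule for it.

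**Conclusion.** The point holds in a conditional form. The sole primary outcome is not the listed assay that tests the protocol's stated mechanism most directly, and no reason is given. At 20 per arm the trial reliably detects only a difference of about 0.91 SD or more. If ADP responds less than AA to COX-1 inhibition, a real ketorolac effect could be missed in the primary conclusion, while remaining visible in the AA secondary outcomes.

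This rests on one step outside the text (AA as the COX-1 substrate), a two-sided 5% t test, and assumed effect sizes. The documents cannot show how probable a miss is. The missing rationale and the missing rule for discordant results do not depend on any of these assumptions.

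**What to change.** Before unblinding, amend the Endpoints section so that AA-agonist aggregometry 10 minutes after vial A is the primary outcome. Make ADP-agonist aggregometry the first secondary outcome, tested next in fixed order, so that both can be tested at 0.05 without adjustment. Label the ADP result as showing whether inhibition extends beyond the COX-1 pathway.

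If ADP stays primary, give the reason, and state that a null ADP result with a positive AA result will not be reported as absence of platelet inhibition.

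Under either choice, restate the Sample Size Justification for the chosen endpoint, with its expected difference, SD and sidedness.

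Cost: ADP loses primary status, and the sample-size statement needs new inputs, because the epinephrine PFA figures support neither agonist. No new assay type or patients are needed for the re-ranking itself: both agonists are listed outcomes, and the Brief Study Protocol schedules aggregometry at both draws. It does not name the agonist at either draw, so the amendment should say that both are run each time. It should also reconcile the baseline, which Endpoints places at the end of the case and the Brief Study Protocol places before surgery.

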Baseline platelet count, platelet count, coagulation parameters (APTT, PT, Fibrinogen), platelet aggregometry, TEG, TEG Platelet mapping and Platelet phosphorylation (pDrp1) parameters will be measured pre-operatively on the day of surgery. A total volume of 18.9 ml of blood will be withdrawn for the study at this time. Routine lab work obtained at this time will require 10 ml of blood, while study related tests will require 8.9 ml. Each patient will undergo either spinal or combined spinal epidural anesthesia with our standard cesarean induction dose of hyperbaric intrathecal 0.75% bupivacaine 1.5 ml, intrathecal fentanyl 25 micrograms and intrathecal morphine 250 micrograms. The patient will be moved to the supine position with left lateral uterine displacement. When a T6 sensory level to pinprick is achieved, cesarean delivery will be allowed to proceed. The vial A will be administered during skin closure near the completion of the case. Platelet aggregometry, TEG, TEG Platelet mapping and Platelet phosphorylation (pDrp1) parameters will be performed 10 min after study drug administration. While under the effect of the spinal medication, meaning that the patient is unable to feel sharp in their feet, the patient may elect to have this blood and the subsequent blood drawn from their foot to avoid unnecessary pain. These blood draws would only be performed by an anesthesiologist and only if a suitable site were identified. Performing venipuncture for lab draws in the feet is not known to increase the risk of complications from blood draws when compared to the upper extremity. An additional volume of 18.9 ml of blood will be withdrawn for the study at this time. After blood samples have been obtained, patients in each group will receive the vial B containing the alternate therapy (i.e. placebo group receives ketorolac and ketorolac receives placebo),

allowing both groups to benefit from the analgesic effect of ketorolac. Supplemental analgesia will be administered according to a standard post-operative pain management protocol on labor and delivery.

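### The protocol gives two incompatible baseline times for the primary assay (ADP aggregometry), and the end-of-case one has no stated sample and is not clearly before the study drug

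*Combined protocol and SAP*

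**What the plan says.** All references are to the combined protocol and SAP, section B3.

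- **Endpoints, on the primary assay:** "Platelet Aggregometry (ADP-agonist) will be performed before (baseline obtained at completion of the case) and 10 min after IV dosing".
- **Endpoints, secondary outcomes:** the baseline for thromboelastography is placed elsewhere: "TEG will be performed before (baseline obtained pre-operatively". The sentence does not go on to give a post-dose time.
- **Brief Study Protocol, baseline:** "platelet aggregometry, TEG, TEG Platelet mapping and Platelet phosphorylation (pDrp1) parameters will be measured pre-operatively on the day of surgery". Aggregometry is in the same list as every other assay.
- **Brief Study Protocol, first dose:** "The vial A will be administered during skin closure near the completion of the case".
- **Brief Study Protocol, second sample:** the same assays "parameters will be performed 10 min after study drug administration", with the volume given as "An additional volume of 18.9 ml of blood will be withdrawn for the study at this time".
- **Data Analysis:** within-group before/after changes are tested with paired tests, and percentage change from baseline is calculated for each aggregometry parameter. Between-group comparisons use unpaired tests, but the section does not say whether these are applied to the 10-minute values or to changes. No baseline adjustment is planned.

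**The concern.** The baseline is half of the primary measurement, and the protocol defines it in two ways. Staff working from Endpoints would draw at the end of surgery. Staff working from Brief Study Protocol would draw before surgery. The two baselines yield different within-arm quantities.

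The end-of-case version has a further problem. Vial A is given during skin closure, which precedes the end of the case. A draw made literally at completion could therefore follow the drug. The protocol's own reason for sampling at 10 minutes is that the drug acts fast: "known platelet inhibition correlates closely with C max", with the peak put at 2.9 ± 1.8 minutes. A baseline taken a few minutes after vial A could already carry much of the effect it is meant to precede. Baseline samples cannot be retaken once the drug has been given.

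**Working it through.** **1. The sources side by side**

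| Item | Endpoints | Brief Study Protocol |
|---|---|---|
| Aggregometry baseline | Completion of the case, and before dosing | Pre-operative, day of surgery |
| Thromboelastography baseline | Pre-operative | Pre-operative |
| Vial A | Not timed | During skin closure |
| Post-dose aggregometry | 10 min after dosing | 10 min after dosing |

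Three statements cannot all be met literally: the baseline precedes dosing, the baseline is at completion of the case, and dosing is during skin closure.

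**2. Is there a sample for an end-of-case baseline?** The pre-operative volume is 10 ml routine + 8.9 ml study = 18.9 ml, which agrees with the stated total. The only other stated volume is the 18.9 ml at 10 minutes post-dose. No volume is given for a draw at completion of the case.

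**3. What each baseline does to each comparison.** Let D be the ketorolac effect on the 10-minute value. Let S be the change from pre-operative to 10 minutes post-dose that is due to surgery, blood loss and fluids, equal in expectation in the two arms by randomization. Let s be the small remaining change from the end of surgery. Let f be the fraction of D already present when the baseline is drawn.

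| Baseline | Ketorolac change | Placebo change | Difference in changes | Difference in 10-min values |
|---|---|---|---|---|
| Pre-operative | S + D | S | D | D |
| End of case, before vial A | s + D | s | D | D |
| End of case, after vial A | s + (1 − f)D | s | (1 − f)D | D |

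If only a proportion q of patients is drawn after vial A, the mean difference in changes is (1 − qf)D.

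**4. Could f be large?** I read 2.9 ± 1.8 minutes as time to peak. One SD either side is 2.9 − 1.8 = 1.1 to 2.9 + 1.8 = 4.7 minutes. On the protocol's premise that inhibition follows peak concentration, a draw a few minutes after vial A could have a large f. The documents do not give the interval from vial A to completion of the case, so f cannot be estimated.

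**5. Illustration only.** The sample-size figure (14 per group) rests on PFA closure time and does not take baseline timing as an input, so it gives no aggregometry effect to work from. Assume instead a difference in changes that has 80% power at 20 per arm, two-sided 0.05: d = (1.960 + 0.842) × √(2/20) = 0.886 SD. Power on the change is then Φ[(1 − f) × 0.886/√(2/20) − 1.960] = Φ[(1 − f) × 2.802 − 1.960].

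| f (or qf) | Power |
|---|---|
| 0 | 80% |
| 0.25 | 56% |
| 0.5 | 29% |
| 0.75 | 10% |
| 1 | type I error level only |

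A mixture of pre-dose and post-dose baselines would also add variance, which this formula ignores.

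**The case against.** The strongest reply is that the protocol never schedules a post-dose baseline. The Endpoints sentence says the sample comes before dosing, and Brief Study Protocol itself describes skin closure as near the end of the case. A draw at the end of surgery just ahead of vial A is an ordinary reading. The literal reading also strains: if closure ran more than 10 minutes past vial A, the baseline would come after the post-dose sample. This stands. A reader might infer that the end-of-case baseline does fall after the drug. The documents support only that it could, because nothing in the wording prevents it.

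Second, the trial is placebo-controlled and its hypothesis is stated against placebo. An unpaired comparison of the 10-minute values ignores the baseline and keeps the whole effect under every reading. This also stands, but Data Analysis does not commit to that comparison as primary.

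Third, a reader might infer that a pre-operative baseline biases the trial because surgery lies between the samples. It does not bias the between-arm contrast, since both arms share S. It does mean that a within-arm before/after test in the ketorolac arm cannot be read as a drug effect. Section B2 itself names blood loss and hemodilution as possible influences on platelet function.

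Fourth, the count of two draws is not fully firm. The sentence allowing foot venipuncture under the spinal refers both to the post-dose sample and to subsequent blood. It gives no time or volume for that blood, so it does not supply an end-of-case baseline.

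Finally, a reader might take 29% as the trial's power. The documents give no basis for that: the effect size and f are both assumed.

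**Conclusion.** The contradiction is certain and concerns the primary assay: completion of the case in one section, pre-operative in the other, with a stated sample for the second only. Whether any patient would have had a baseline after vial A is conditional on the end-of-case clause being followed literally.

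If so, the paired tests, the percentage change and any between-arm comparison of changes shrink by the factor 1 − qf, while the comparison of 10-minute values is unaffected. The size of the loss cannot be fixed from the documents. If the pre-operative baseline is used, no drug effect is lost, but only the between-arm contrast isolates ketorolac. The point needs settling before samples are drawn, because the wording decides which blood is taken and when.

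**What to change.** Reconcile Endpoints and Brief Study Protocol to one baseline draw that precedes vial A in every patient, and state it identically in both places. This concerns sampling time only.

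**Simplest option:**

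1. Delete the bracketed end-of-case clause from the primary outcome sentence and keep the pre-operative draw.
2. In Data Analysis, name the primary analysis as the between-arm difference in the 10-minute ADP aggregometry value, adjusted for the pre-operative value (ANCOVA).
3. Present within-arm changes and percentage changes as descriptive.
4. Complete the thromboelastography timing sentence so that it matches.

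The cost is wording in three places. Both samples are already planned, so no extra blood is needed.

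**Alternative:** an end-of-surgery baseline, drawn before vial A, would largely keep surgery out of the within-arm change. It is not free. The pre-operative collection includes 10 ml of routine bloods and the platelet count, and Subject Selection excludes patients on that count. That collection would still be needed, and the study portion (8.9 ml) would become a separate third collection, which the blood volumes in Brief Study Protocol would have to show. The ANCOVA is sound here too, provided the draw is recorded as pre-dose in every patient.

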**Brief Study Protocol**

After obtaining IRB approval, patients will be randomly assigned to receive either IV ketorolac 30 mg (n=20) or normal saline (n=20) based on a pre-assigned randomization sequence. The assignment for each patient will be kept in the research pharmacy. After obtaining written informed consent, research pharmacy will provide the team with two syringes, ketorolac and placebo. The vials will be labeled vial A and B. If the patient is assigned to receive ketorolac, syringe A will contain ketorolac and syringe B will contain normal saline placebo. For patient assigned to the placebo arm, syringe A will contain normal saline and syringe B will contain ketorolac. The patient and the study investigators will be blinded to the study drug.

Baseline platelet count, platelet count, coagulation parameters (APTT, PT, Fibrinogen), platelet aggregometry, TEG, TEG Platelet mapping and Platelet phosphorylation (pDrp1) parameters will be measured pre-operatively on the day of surgery. A total volume of 18.9 ml of blood will be withdrawn for the study at this time. Routine lab work obtained at this time will require 10 ml of blood, while study related tests will require 8.9 ml. Each patient will undergo either spinal or combined spinal epidural anesthesia with our standard cesarean induction dose of hyperbaric intrathecal 0.75% bupivacaine 1.5 ml, intrathecal fentanyl 25 micrograms and intrathecal morphine 250 micrograms. The patient will be moved to the supine position with left lateral uterine displacement. When a T6 sensory level to pinprick is achieved, cesarean delivery will be allowed to proceed. The vial A will be administered during skin closure near the completion of the case. Platelet aggregometry, TEG, TEG Platelet mapping and Platelet phosphorylation (pDrp1) parameters will be performed 10 min after study drug administration. While under the effect of the spinal medication, meaning that the patient is unable to feel sharp in their feet, the patient may elect to have this blood and the subsequent blood drawn from their foot to avoid unnecessary pain. These blood draws would only be performed by an anesthesiologist and only if a suitable site were identified. Performing venipuncture for lab draws in the feet is not known to increase the risk of complications from blood draws when compared to the upper extremity. An additional volume of 18.9 ml of blood will be withdrawn for the study at this time. After blood samples have been obtained, patients in each group will receive the vial B containing the alternate therapy (i.e. placebo group receives ketorolac and ketorolac receives placebo),

allowing both groups to benefit from the analgesic effect of ketorolac. Supplemental analgesia will be administered according to a standard post-operative pain management protocol on labor and delivery.

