### ***Data Analysis:***

Data will be assessed for normality using Q-Q normality plots and the Kolmogorov-Smirnov test. Demographic, obstetric, and perioperative data will be presented as mean (SD) or median [interquartile range]. Between-group comparisons will be assessed using the unpaired t test and Mann-Whitney U test, where appropriate. Within-group before vs. after NSAID exposure changes will be assessed using the paired t test and Wilcoxon signed rank test, where appropriate. The percentage change from baseline for each Platelet Aggregometry, TEG, and lab parameter will also be calculated.

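### PT, PTT, INR and fibrinogen are secondary outcomes with a planned change from baseline, but the post-dose panel omits them although the blood volume is unchanged

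*Combined protocol and SAP*

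**What the plan says.** Three parts of the combined protocol and SAP bear on this point.

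- **Outcomes (B3.A, Endpoints).** The secondary outcomes include "laboratory coagulation indices (PT, PTT, INR, fibrinogen").
- **Analysis (B3.B, Data Analysis).** "The percentage change from baseline for each Platelet Aggregometry, TEG, and lab parameter will also be calculated". The same paragraph plans paired tests: "Within-group before vs. after NSAID exposure changes will be assessed using the paired t test and Wilcoxon signed rank test, where appropriate".
- **Sampling (B3.A, Brief Study Protocol).** Before surgery: "Baseline platelet count, platelet count, coagulation parameters (APTT, PT, Fibrinogen), platelet aggregometry, TEG, TEG Platelet mapping and Platelet phosphorylation (pDrp1) parameters will be measured pre-operatively". After dosing: "Platelet aggregometry, TEG, TEG Platelet mapping and Platelet phosphorylation (pDrp1) parameters will be performed 10 min after study drug administration".

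The Brief Study Protocol also gives the volumes. For the baseline draw it says "A total volume of 18.9 ml of blood will be withdrawn for the study at this time" and splits this figure: "Routine lab work obtained at this time will require 10 ml of blood, while study related tests will require 8.9 ml". For the post-dose draw it says only "An additional volume of 18.9 ml of blood will be withdrawn for the study at this time", with no split and no mention of routine laboratory work.

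**The concern.** A change from baseline and a paired before/after test each need two values per patient. For the coagulation indices the sampling schedule supplies one, taken before any study drug. A between-arm comparison of that single value says nothing about ketorolac, because under randomisation any pre-dose difference between the arms is chance.

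The gap could not be closed afterwards with a later sample. Once the 10-minute blood has been taken, each patient receives the alternate syringe, so the placebo arm then receives ketorolac. The 10-minute draw is the only planned point at which treated and untreated patients can be compared.

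The volumes raise a second question. The post-dose list is shorter than the baseline list, yet the volume is the same. Either the list is incomplete or the volume is not the one that the listed tests need.

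**Working it through.** **Step 1. Compare the panels.**

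| Test | Secondary outcome (Endpoints) | Pre-operative panel | 10-minute panel |
|---|---|---|---|
| PT | yes | yes | not listed |
| PTT (APTT) | yes | yes | not listed |
| INR | yes | not named | not listed |
| Fibrinogen | yes | yes | not listed |
| Platelet count | no | yes | not listed |
| Aggregometry | yes (AA agonist; the ADP agonist is primary) | yes | yes |
| TEG | yes | yes | yes |
| TEG platelet mapping | yes | yes | yes |
| pDrp1 | yes | yes | yes |

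The post-dose panel is the baseline panel without platelet count, APTT, PT and fibrinogen. All four coagulation outcomes therefore lack a listed post-dose measurement. INR is not named at baseline either, although PT, from which it is derived, is. No other section schedules a coagulation sample after dosing.

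**Step 2. Reproduce the stated baseline volume.**

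Routine share + study share = 10 + 8.9 = 18.9 ml, which agrees with the plan.

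**Step 3. Compare the post-dose volume with its panel.**

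The stated post-dose volume is 18.9 ml, so the two draws total 18.9 + 18.9 = 37.8 ml. The volume needed for the post-dose tests alone is not given. It depends on how tests fall between the two baseline shares, which the plan does not state:

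- *The four listed tests make up exactly the study-related share (assumption).* They need 8.9 ml. Volume with no stated use: 18.9 − 8.9 = 10.0 ml per patient. The two draws would total 18.9 + 8.9 = 27.8 ml.
- *Some coagulation tests also sit in the study-related share.* The listed tests need less than 8.9 ml, and the volume with no stated use exceeds 10 ml.
- *Some of the listed tests sit in the routine share.* The listed tests could need more than 8.9 ml, and the volume with no stated use would be below 10 ml.
- *The full baseline panel was meant to be repeated.* All 18.9 ml is used and the volume with no stated use is 0 ml. The error is then in the list alone.

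The first reading is the natural one if the post-dose list is complete, because those four tests are the trial's research assays. Whatever the allocation, a shorter list carries an unchanged volume.

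**The case against.** The strongest reply is that the plan's intent is clear and one sentence is incomplete. The unchanged 18.9 ml, the listing of coagulation indices as outcomes and the planned change for each laboratory parameter all suggest that the full panel was to be repeated. On that reading no outcome is lost and no blood is unused. This may well be what was meant, and it is one of the two ways to resolve the point. It does not remove the contradiction, because staff who follow the listed panel would not run these tests.

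A second reply is that the consequence is limited. That stands. The hypothesis concerns platelet function, and aggregometry, TEG, platelet mapping and pDrp1 all have a scheduled post-dose measurement.

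A reader might also infer more than the documents support:

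- *That the post-dose tests need 8.9 ml, so that 10 ml per patient is certainly drawn without purpose.* Only the baseline draw is split, and no test is assigned to either share.
- *That a fixed fraction of the secondary outcomes is lost.* The TEG indices are introduced by the word including, so the list is open and has no firm denominator.
- *That without a post-dose platelet count, hemodilution cannot be told apart from a drug effect.* The concurrent randomised placebo arm has the same surgery and the same sampling time, so hemodilution is expected to balance between arms. Estimated blood loss and intraoperative fluid volume are also recorded. Platelet count is not a listed outcome, so its absence after dosing is not part of this contradiction.

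**Conclusion.** The contradiction holds. Four named secondary outcomes (PT, PTT, INR and fibrinogen) have a planned change analysis and no scheduled post-dose measurement. Followed as written, neither a change from baseline nor a treatment effect can be computed for any of them. This conclusion rests on the text alone and needs no assumption.

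The mismatch in volume also holds: a shorter panel carries the same 18.9 ml. Its size is conditional. It is about 10 ml per patient if the four listed tests correspond to the study-related share, and 0 ml if the full panel was meant to be repeated. It would be wrong to conclude that outcomes are lost and blood is wasted together. That requires the larger volume to be drawn and the laboratory tests not to be run, which is the least plausible reading.

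The primary outcome and the sample size are not affected. The point should be settled because it is cheap to do so before sampling and cannot be repaired once the alternate syringe has been given.

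**What to change.** Reconcile Endpoints, Brief Study Protocol and Data Analysis in one of two ways.

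1. **If the coagulation indices are to remain outcomes:** add PT/INR, PTT and fibrinogen to the 10-minute panel and name INR in the baseline panel as well. The stated 18.9 ml appears to cover this, so the cost is a change of wording and the laboratory runs on blood already planned to be drawn.
2. **If they are only a pre-operative check:** remove them from the secondary outcomes and from the percentage-change analysis, and restate the post-dose volume for the panel actually run. That volume should come from the tube requirements of the listed tests. The 8.9 ml figure should not be carried over unless the team confirms that it belongs to those tests. The cost is wording and the removal of four outcomes.

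Under either option, state which tests make up each part of the blood volume at each draw, so that the panel and the volume can be checked against each other.
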